#### 12.4.1.2 *Secondary efficacy variables (MP only)*

The difference between treatment groups in the change from baseline in AS score for each treated clinical patterns (e.g., flexed elbow, flexed wrist, flexed fingers) of the UL at all other post baseline visits will be analyzed by a MMRM analysis as described for the primary efficacy variable.

Pain intensity (from subjects) and pain frequency (from parent/caregiver) assessed with QPS will be analyzed by using frequency tables and descriptive summary statistics at all visits and for changes from baseline to all post-baseline visits.

Child's/Adolescent's (if applicable) and Parent's/Caregiver's GICS at Day 29 (Week 4) will be analyzed descriptively by an analysis of covariance model as described for the co-primary efficacy analysis.

These tests will be descriptive and interpreted in an explorative manner. Treatment comparisons will be tested for comparison of the high versus low dose treatment group and the mid versus low dose treatment group, respectively. Furthermore descriptive summary statistics will be performed for all secondary efficacy variables at all visits and for the changes from baseline to all post-baseline visits. Summary statistics are defined as N, mean, standard deviation, median, 1st and 3rd quartile, minimum and maximum or/and as counts and percentages.

MMRM analysis as well as observed case analyses and LOCF of the secondary efficacy variable AS will be performed on the FAS and PPS of MP. For these variables LOCF is considered as conservative approach. Handling of missing data of MP for further secondary efficacy variables will be defined in the SAP.

[REDACTED]

#### **12.4.2 Pharmacodynamic variables**

Not applicable.

#### **12.4.3 Pharmacokinetic variables**

Not applicable.

#### **12.4.4 Pharmacogenetic variables**

Not applicable.

#### **12.4.5 Safety variables**

All safety analyses will be performed on the SES of MP and OLEX using descriptive summary statistics, frequency tables, and, if applicable, shift tables and shift graphs. Analyses will be based on both, total population and by MP treatment group.

#### **Adverse events**

Analyses of adverse events will be performed for total dose group in addition to total population and MP treatment group. AEs will be coded by system organ class and preferred term level according to the MedDRA version in effect at the time the respective databases of MP and of OLEX Period, respectively, are closed. Only TEAEs will be analyzed. Non-TEAEs are defined as baseline complaints and will be listed only.

For MP, only TEAEs of the MP will be analyzed, which are defined as AEs with onset or worsening on or after date and time of the first MP administration and before date and time of the first OLEX administration at V6. For subjects who do not receive an OLEX administration all AEs with onset or worsening on or after date and time of the first MP administration will be considered as TEAEs of MP.

-AEs starting in MP and not having resolved at the Final Visit V5 of MP will be followed and further documented during OLEX.

For OLEX period, only TEAEs of the OLEX will be analyzed, which are defined as AEs with onset or worsening on or after date and time of the first OLEX administration at V6. Frequencies will be calculated for TEAEs on the system organ class level and on the preferred term level. For all TEAEs the occurrence, worst intensity, final causal relationship to treatment assessed by investigator, and final outcome will be summarized by counts and percentages for all visits and overall. Listings and, if applicable, tables displaying frequencies of TEAEs leading to discontinuation, TESAEs, TEAESIs, and deaths will also be provided.

Additional subgroup analyses (e.g., classes for GMFCS level, age groups, use of anesthesia/analgo-sedation for injection treatment) will be specified in detail in the SAP.

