## 12 STATISTICAL METHODS

This section describes the statistical analyses foreseen at the time of study planning. Further details on the statistical and analytical aspects will be presented in the SAP.

Any deviations from planned analyses, the reasons for such deviation, and all alternative or additional statistical analyses that may be performed before database close/unblinding of MP or database close of OLEX, respectively, will be described in amendments to the clinical study protocol or the SAP. All deviations and/or alterations will be summarized in the clinical study report including MP and OLEX.

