7.5 Safety Variables

All safety analyses of the MP will be performed on the SES of the MP. All safety analyses of the OLEX Period will be performed on the SES of the OLEX period. Analyses will be based on both, total population and by Main Period treatment group (high, mid, low). For this purpose the Main Period treatment group as treated instead of as randomized will be used. In the unlikely case that a subject has received mid or low dose instead of the planned high dose during the OLEX Period, he/she will be analyzed in total group of the OLEX tables together with all other subjects with the correct high dose treatment.

For safety variables the last measurement before start of treatment is defined as baseline value.

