 - start date/time completely missing and end date/time not before date/time of first exposure in the MP, set start date/time to date/time of first exposure in the MP
 - if AE end date and time are missing set end date to study end date (i.e. last contact or last visit of the study) and end time to 23:59
 - if AE end date/time is partially missing, set end day to last day of the given month or end day/month to 31/12 of the given end year and missing end time to 23:59
 - if AE end time is missing set time to 23:59.

Imputation rules for multiple records in case of AE worsening:

- For missing AE start date/time the imputation strategies as defined above will be applied to all records of the same AE.
- For missing TEAE end date/time the imputation strategies as defined above will be applied to the last record of the same TEAE.

Calculation of time to onset/duration of AEs [days]:

- Time to onset of an AE is defined as start date of AE - date of most recent administration of study drug [+ 1 for AE starting after start of treatment]
- The duration will be calculated as stop date - onset date + 1 for each episode of worsening.

Incidences will be calculated for TEAEs overall (MP+OLEX), overall OLEX and by injection cycle on the system organ class (SOC) level and on the preferred term (PT) level (i.e., total, by worst intensity, by worst relationship, and by worst outcome). Listings and, if applicable, tables displaying incidences for TEAEs leading to discontinuation, serious TEAEs, related serious TEAEs, TEAEs of special interest, and deaths will also be provided. Additionally the number and percentage of subjects with at least one non-serious TEAE with incidence $\geq 5\%$

in any MP treatment group or in the OLEX Period and number of non-serious TEAE will be displayed by SOC level and PT level. Time to onset and duration of AEs will be listed. Time to onset and duration of AEs will be listed.

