7.7.5 Examination of Subgroups

Subgroup analyses will be performed for the AS regarding treatment group, pooled sites, BoNT-A pre-treatment status, GMFCS-E&R level groups at Screening, AS baseline value, age (2-5, 6-11, 12-17 years), weight group at baseline (<25 kg, \geq 25 kg), use of local anesthetics and/or analgosedation and unilateral versus bilateral treatment. Shift tables and frequency tables of changes will not be presented for subgroup analyses.

Subgroup analysis for TEAEs, related TEAEs, serious TEAEs and TEAEs of special interest by SOC and PT will be performed for the following subgroups: GMFCS-E&R level groups, age (2-5, 6-11, 12-17 years), weight group at baseline (<25 kg, \geq 25 kg), and use of local anesthesia/analgosedation for injection treatment.

The following TEAESIs will be analyzed by UL treated, LL treated, not applicable (not located at any treated limb):

- Muscular weakness

- Monoparesis
- Hemiparesis
- Paralysis
- Paralysis flaccid
- Paraparesis
- Paresis
- Peripheral nerve palsy
- Peripheral paralysis
- Quadriparesis

For this analysis “UL treated” means that the AE is located at an upper limb, which was treated. “LL treated” means that the AE is located at a lower limb, which was treated. “Not applicable” means that the AE is not located at any treated limb.

For the subgroup analysis ‘use of local anesthetics and/or analgosedation’ the two following subgroups will be analyzed:

- Subjects with use analgesics and/or sedatives been used during corresponding injection
- Subjects without use analgesics and/or sedatives been used during corresponding injection

For the subgroup analysis regarding ‘unilateral versus bilateral treatment’ the following subgroups will be defined for analysis of the AS score of the ULs:

- Unilateral treatment of the upper limbs (Treatment combination A if unilateral, B, C and D)
- Bilateral treatment of the upper limbs (Treatment combination A if bilateral and E)

For analysis of the AS score of the LLs the following subgroups will be analyzed:

- Unilateral treatment of the lower limbs (Treatment combination B)
- Bilateral treatment of the lower limbs (Treatment combination C, D and E)

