The primary clinical target pattern will be set to missing for subjects whose primary clinical target pattern was not treated in the MP by mistake. As a consequence these subjects will not have the primary efficacy variable "change from baseline in AS in the primary clinical target pattern". If these subjects have a measurement for the Investigator's GICS for upper limb at Day 29 these subject still belong to the FAS of the MP. According to the definition of the FAS of the OLEX from the CSP, subjects without primary clinical target pattern will be excluded from the FAS of the OLEX. But it is more reasonable to evaluate all subjects for the OLEX for whom at least one post-baseline value of any efficacy variable in the OLEX is available. In agreement with the intention-to-treat principle the Full Analysis Set of the OLEX should be as "full" as possible. For this reason the definition of the FAS of the OLEX will be changed to the following definition: The FAS of the OLEX is the subset of subjects in the SES of the OLEX for whom at least one post-baseline value of any efficacy variable in the OLEX is available. As a consequence subjects without primary clinical target pattern will no longer be excluded from the OLEX.

Investigator's, Child's/Adolescent's (if applicable) and Parent's/Caregiver's GICS [REDACTED] will be analyzed by descriptive summary statistics and frequency tables [REDACTED] instead of analysis of covariance (ANCOVA) for the OLEX Period. An ANCOVA is not appropriate for the OLEX period since all subjects receive the same treatment and no treatment differences can be estimated.

Other efficacy variables:

For other efficacy variables in the SAP the visit numbers were added and the variables were given in more detail than in the protocol.

Further other variables:

Planned treatment of spasticity, treatment compliance, monitoring during sedation, injection guidance technique, length of injection cycle, and extent of exposure were added to other variables.

Safety variables:

The secondary efficacy variable occurrence of TEAEs by final outcome in the CSP was changed to occurrence of TEAEs by worst outcome in the SAP. Usually final outcome is the same as worst outcome. But it may occur that a subject has two different TEAEs at two different time points, which are coded with the same PT (e.g. left leg broken and right leg broken). Then it is more important to know the worst outcome of both TEAEs than only the outcome of the second TEAE.

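### The supplied SAP text leaves out, undefined and undeclared, the protocol's adverse event analysis by total dose group, and its two lists of special-interest terms disagree on 'Paralysis flaccid'

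*Protocol*

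**What the plan says.** **Total dose group.** Protocol 12.4.5 opens with a rule for all safety data: "Analyses will be based on both, total population and by MP treatment group". Its adverse event paragraph then adds a further grouping: "Analyses of adverse events will be performed for total dose group in addition to total population and MP treatment group". The supplied text uses the term nowhere else and gives no categories or cut-points.

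SAP 7.5 repeats only the general rule: "Analyses will be based on both, total population and by Main Period treatment group (high, mid, low"). SAP 7.5.2 sets the layout of the tables of treatment-emergent events (TEAEs): "Incidences will be calculated for TEAEs overall (MP+OLEX), overall OLEX and by injection cycle on the system organ class (SOC) level", and by preferred term. SAP 7.7.5 begins "Subgroup analysis for TEAEs, related TEAEs, serious TEAEs and TEAEs of special interest by SOC and PT will be performed for the following subgroups" and names GMFCS level, age, weight group (below 25 kg or not) and use of anaesthesia or analgosedation. Total dose and treatment combination are not among them.

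Protocol section 12 says that deviations from the planned analyses "will be described in amendments to the clinical study protocol or the SAP". SAP section 8 declares three safety changes. One is that "occurrence of TEAEs by final outcome in the CSP was changed to occurrence of TEAEs by worst outcome in the SAP"; the others are the suicidality screening and the C-SSRS. Total dose group is not mentioned.

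**Special-interest terms.** Protocol Table 18 (MedDRA 15.1) includes 'Paralysis flaccid'. SAP 7.5.2 refers to SAP Table 1 (MedDRA 21.0) for the list of special-interest events (TEAESIs), and the term is absent there. SAP 7.7.5 nevertheless names it among ten TEAESIs to be tabulated by treated limb.

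**The concern.** The protocol commits to the third grouping; it is not offered as an example. It cannot mean the pooled column or the randomised arm, because the same sentence names both separately. A programmer working from the supplied SAP text could not produce it.

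The consequence falls mainly on OLEX. Every child there is scheduled for the high-dose regimen whatever the main period (MP) arm, yet the columns remain by MP arm. They therefore describe past randomisation and not the total body dose scheduled in the cycle where the event arose. The pooled column does not help either: of a child given the wrong dose in OLEX, SAP 7.5 says "he/she will be analyzed in total group of the OLEX tables together with all other subjects with the correct high dose treatment". The protocol caps total body dose for safety reasons and reports no monitored paediatric experience with this product, so a reader would want to see events against total dose.

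The term mismatch could leave the overall TEAESI table and the by-limb table counting different events.

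**Working it through.** The plan states no figure on this point to reproduce. The check is a comparison of text, dose tables and term lists.

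**1. Scheduled total body dose from 25 kg (protocol Tables 7, 9, 11 and 13).** Mid and low are 75% and 25% of high.

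| Combination | High | Mid (×0.75) | Low (×0.25) |
|---|---|---|---|
| A unilateral | 200 U | 150 U | 50 U |
| A bilateral, B, D | 400 U | 300 U | 100 U |
| C, E | 500 U | 375 U | 125 U |

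This gives nine distinct totals in MP. OLEX uses the high column only, so it has three: 200, 400 and 500 U (8, 16 and 20 U/kg below 25 kg). The ratio is 500/200 = 20/8 = 2.5, and this range can occur inside every MP-arm column. A former low-arm child in combination C is scheduled for 500 U and shown under low. A former high-arm child in unilateral A is scheduled for 200 U and shown under high.

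The 500 U figure is taken from the tables. The sentence after Table 11 in protocol 8.1.1.2 gives a 400 U maximum beside the 20 U/kg total. The two must be reconciled before the top class is fixed.

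**2. Does GMFCS level stand in for total dose?** Only partly. Levels IV-V can be in A, B or D, hence 200 or 400 U. Levels I-III can be in A, B, C or E, hence 200, 400 or 500 U.

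**3. How well does scheduled class reflect exposure?** Imperfectly from 25 kg, where units are fixed. With 25 and 60 kg as illustrative weights:
- 500 U: 500/25 = 20 U/kg; 500/60 = 8.3 U/kg.
- 200 U: 200/25 = 8 U/kg; 200/60 = 3.3 U/kg.

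The top class at 60 kg and the bottom class at 25 kg are nearly equal per kg.

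**4. Would pooled dose bands help in MP?** Little. Suppose the nine totals are banded as up to 125, 150-200, 300-375, 400 and 500 U. The first band is the whole low arm, the third is all mid, and the last two are all high. Only 150-200 U mixes arms (unilateral A, mid and high). Four of the five bands are an arm or a slice of one.

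**5. Term lists, compared term by term.**
- Protocol Table 18 has 50 terms and SAP Table 1 has 49.
- Protocol only: 'VIIth nerve paralysis' and 'Paralysis flaccid'. SAP only: 'Facial paralysis'.
- If 'VIIth nerve paralysis' and 'Facial paralysis' are one term re-worded (an assumption), 'Paralysis flaccid' is the single unmatched term.
- Of the ten by-limb terms in SAP 7.7.5, nine are in SAP Table 1 and all ten are in protocol Table 18.

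**The case against.** **The first point argues from silence.** Tables by group would naturally be enumerated in SAP Appendix 1, which was not supplied. This stands. A reader might infer that the sponsor withdrew a promised safety analysis, but the documents do not support that: a table may be listed in Appendix 1, and the silence may be oversight. What survives is that the supplied methods text neither defines the group nor declares its absence, while SAP section 2 sets out to be precise enough for programming. The SAP safety sections show no redaction that would explain the gap.

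**The dose classes are an interpretation.** This also stands. The protocol tabulates the totals but never says that they are what total dose group means. The 2.5-fold range shows what that reading would separate; it does not measure an error in the plan.

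**Related information is already planned.** AE subgroups by GMFCS level and weight are specified, and SAP 7.6 summarises injected units. It would be wrong to infer that dose goes unreported. However, the supplied text does not cross injected units with AEs, and GMFCS level carries only part of the information.

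**The term mismatch is one term and may be a leftover from the older dictionary.** This is plausible, since the protocol planned to use the MedDRA version in effect at database close. A version change could explain why the term left Table 1, but not why SAP 7.7.5 still calls it a TEAESI. A reader might infer that events will be miscounted. That does not follow, because neither document says whether the term can be coded in version 21.0. Tables by system organ class and preferred term would count the event as a TEAE in any case.

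**Conclusion.** Both points hold and are minor.

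1. The protocol commits to AE analysis by total dose group. The supplied SAP text has no such analysis, no definition and no declared change. Confidence is medium because Appendix 1 was not seen. The practical effect is mainly in OLEX, where former-arm columns do not reflect scheduled total body dose. Its size rests on reading the group as scheduled dose class and on the protocol's dose tables being correct.

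2. SAP Table 1 and SAP 7.7.5 disagree on one term; confidence is high. If the term can be coded in MedDRA 21.0, such an event would be in the by-limb table but not in the overall TEAESI table. If it cannot, the row in 7.7.5 is an empty leftover.

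A reader might suspect that the randomised safety comparison is compromised. It is not: AEs by MP arm are planned. Efficacy and type I error are also unaffected, and all the outputs concerned are descriptive.

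**What to change.** **Total dose group.**
- Check Appendix 1 first. If it already defines the group and lists the tables, only a cross-reference from the methods text is needed.
- Otherwise reconcile the 400 U in the sentence after protocol Table 11 with the 500 U in that table, then define the group in SAP 7.5.2 and 7.7.5. One workable definition for OLEX is the scheduled total body dose class as tabulated in the protocol: 8 U/kg or 200 U, 16 U/kg or 400 U, 20 U/kg or 500 U.
- Add descriptive OLEX tables of TEAEs, related TEAEs, serious TEAEs and TEAESIs by that class. Label them as non-randomised, tied to GMFCS level and treatment combination, and not weight-adjusted above 25 kg.
- For MP, show dose class within arm or omit it; pooled bands would nearly reproduce the arms.
- If the analysis is not wanted, declare and justify the omission in SAP section 8.

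**Term list.** Use one list for the overall and by-limb tables. Either restore 'Paralysis flaccid' or its MedDRA 21.0 equivalent in SAP Table 1, or correct SAP 7.7.5. Record the mapping from version 15.1 to 21.0.

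**Cost.** A definition and a few descriptive tables from data already collected, some with small cells, or one paragraph in section 8; plus one table row and a short mapping note.

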## **Other safety variables**

Laboratory evaluations, vital signs, BMI, weight, height, Investigator's Global Assessment of Tolerability, and incidences of subjects with antibodies against BoNT-A will be analyzed descriptively (values and changes from baseline) and screened for individual notable values and/or changes.

### **12.4.6 Other variables**

Subject dispositions, demographic data, and other baseline characteristics such as medical history and concomitant diseases, previous and concomitant therapies, CP history (e.g., distribution, comorbidities), clinical patterns, GMFCS level, BoNT-A pre-treatment status at screening and use of anesthesia/analgesedation for injection treatments will be presented using standard descriptive statistics. No homogeneity tests will be performed.

Demographic data will be summarized for the SES (MP and OLEX), the FAS (MP and OLEX), and the PPS (MP only). Clinical patterns, AS scores at baseline and GMFCS level at Screening will be summarized descriptively for the FAS (MP and – for selected baseline clinical patterns only - OLEX) and the PPS (MP only).

Frequencies of concomitant medication will be given based on different Anatomical Therapeutic Chemical classification [ATC] system of the WHO code levels for the SES (MP and OLEX), the FAS (MP and OLEX), and the PPS (MP only). Indications for concomitant therapies will not be coded and will only be listed. Medical history and concomitant diseases as well as non-drug treatment will be described based on MedDRA system organ class and preferred term levels for the SES (MP and OLEX).

### **12.4.7 Special statistical/analytical issues**

#### **12.4.7.1 Discontinuations and missing data**

Discontinued subjects will not be replaced (see [Section 8.2.1](#)).

The primary and secondary efficacy variables AS will be analyzed on the FAS and PPS of the MP using MMRM for accounting for missing data. As sensitivity analysis for the primary efficacy variable and for the secondary efficacy variables of the AS score an ANCOVA model without repeated measures will be applied. The LOCF will be followed on the FAS and PPS, i.e., the baseline observation will be carried forward to Day 29 (Week 4) of MP and the last non-missing value before a missing value will be carried forward to all further visits with missing values. In addition, further sensitivity analysis for the primary and secondary efficacy variables, the so-called observed case analysis without missing data replacement, will be performed on the FAS and PPS of the MP to explore the impact of the respective missing imputation principle.

In case of missing data in the co-primary variable these will be imputed by "0" (no change). Assuming a similar percentage of missing data in all three treatment arms this

imputation leads to a decreased difference of the treatment effects. For this reason the “no change” imputation is considered as conservative approach. Sensitivity analyses for the co-primary efficacy variable by using the so called ‘observed case analysis’ without missing data replacement will be performed on the FAS and PPS to explore the impact of missing values.

For other secondary [REDACTED] efficacy variables, missing data of the MP will be replaced using an appropriate imputation method specified in detail in the SAP. Missing data will not be replaced for OLEX.

In case further missing value replacement strategies will be applied on any variables these will be described in detail in the SAP before unblinding of the MP data.

